Study protocol

Official Title of the study: Research on New Intelligent Diagnosis and Treatment Technologies for Early Lung Cancer Based on Multimodal Imaging Bronchoscopy Navigation

Affiliation: Sir Run Run Shaw Hospital, Zhejiang University School of MedicineDepartment: Department of Respiratory and Critical Care MedicineDate of the document: May 20, 2024

Research on new intelligent diagnosis and treatment technologies for early lung cancer based on multimodal imaging bronchoscopy navigation

Background

Lung cancer is one of the malignant tumors with the highest incidence and mortality rates worldwide. From the 1970s to the present, the mortality rate of lung cancer in China has been climbing year by year, and currently lung cancer ranks first in China in terms of incidence rate and mortality rate. Meanwhile, data show that 75% of lung cancer patients are already in advanced stage when they are diagnosed. The 5-year survival rate of advanced lung cancer in China is only 16.1%, while the 5-year survival rate of early lung cancer patients can reach 73%. Therefore, improving the early diagnosis rate of lung cancer will greatly reduce the mortality rate of lung cancer.

Regular chest computed tomography (CT) in the population can detect a large number of nodular lung lesions, and data show that lung nodules are detected in approximately 25% of the population on routine screening, most of which (96.4%) are benign. Further examination of these high-risk lung nodules is effective in improving early lung cancer detection and reducing mortality by approximately 20%. CT-guided percutaneous lung puncture is the mainstay of conventional diagnosis of lung nodules, and the risk of complications is a major concern. Its complications include pneumothorax, hemoptysis, and needle tract metastasis, among which the incidence of pneumothorax is 12.3% and hemoptysis is 20%. In recent years, the use of navigational tracheoscopy for peripheral lung nodule biopsy has gradually increased in the clinic due to good safety and accuracy. 2020 CHEST published a meta-analysis on navigational tracheoscopy, the incidence of pneumothorax is only 2%, which is obviously advantageous compared with the traditional methods.

Even so, navigational bronchoscopy techniques have limitations in the management of peripheral lung nodules. Navigation bronchoscopy has limitations in the diagnosis and treatment of peripheral lung nodules. Data show that the overall diagnostic rate of navigation bronchoscopy for biopsy of peripheral lung nodules is 80%, which is lower than that of traditional CT-guided percutaneous lung puncture, especially for near-pleural foci and foci with a diameter of less than 1 cm. There are three reasons for this. First, the current mainstream navigation system based on CT images does not have enough ability to recognize airways smaller than 3 mm, and intraoperative blindness exists in some of the small airway areas, resulting in failure or inaccuracy of preoperative bronchoscopic path planning in some areas. Second, the current mainstream bronchoscopy equipment apex outer diameter is generally around 4-5mm, which cannot enter the finer distal small airways, and it is difficult to reach some peripheral lesions close to the subpleural area, which makes it difficult to increase the biopsy positivity rate of this part of the lesion. Third, the small airways around the lesions are in a collapsed state due to various reasons such as sputum stasis, insufficient inspiration or breath holding during the acquisition of CT images, so it is difficult for preoperative CT to truly reflect the situation of the patient's airway, which ultimately results in the difference between the real-time observation of the distribution of the airway and the pathway of the preoperative planning, and makes it impossible to realize the accurate guidance in the intraoperative period.

To improve the diagnostic rate of lung nodules by navigational bronchoscopy, this project has conducted a preliminary exploration to address the three main issues mentioned above. The preliminary research found that the mainstream whole-lung navigation systems on the market, including The SPiN Thoracic Navigation System magnetic navigation system from Veran, the virtual bronchoscopic navigation (VBN) System from Lungpro of Broncus, and the Super Dimension Electromagnetic Navigation System from Medtronic, are all similar, although there are differences in the operation process. Despite the differences in operation procedures, the core technology of computerized virtual bronchial tree imaging is similar, and all of them are suboptimal for the reconstruction of small airways less than 3 mm. The main reason is that for small airways less than 3 mm, the airway features are not obvious or missing, which are difficult to be extracted by the existing navigation algorithms. To address this problem, on the basis of the existing algorithms to recognize airway segments, deep learning technology is added to do super-resolution reconstruction of the original CT by super-

resolution convolutional neural network (SRCNN), so as to enhance the visual features of the airway smaller than 3mm, and link the 3D-VNET network model with its own attention mechanism to intelligently recognize more small airway segments smaller than 3mm.

Study purpose and design

To improve the problems of recognition, extraction, and three-dimensional reconstruction of 2-3mm small airways that have not been solved by mainstream navigation software on the market through deep learning methods based on the VBN navigation system, and evaluate the accuracy of the improved navigation system and the original navigation system in the diagnosis of peripheral pulmonary lesions (PPL) through a randomized controlled trial.

Study population

Subjects for this single-center randomized controlled trial were recruited from August 2023 to December 2024 at the Sir Run Run Shaw Hospital, Zhejiang University School of Medicine.

Inclusion and exclusion criteria

Inclusion criteria: (1) aged 18 years or above; (2) patients with one or more peripheral lung nodules suspected to be lung cancer or poorly absorbing lesions on conventional anti-infective therapy; (3) patients with nodule diameters \leq 30 mm (diameters mentioned in the text are the average of the maximum and minimum diameters; (4) the nodules were pure ground glass nodules, partially solid nodules, or solid nodules; (5) the nodule is surrounded by lung parenchyma and is not visible in the bronchial lumen above the segment.

Exclusion criteria: (1) preoperative judgment that it is difficult for the patient to benefit from bronchoscopic biopsy (e.g., high risk of bleeding due to perivascular encasement of the lesion, difficulty in reaching the airway adjacent to the lesion due to previous lung surgery, etc.); (2) those with incomplete clinical data; (3) those with missing visits after biopsy.

Interventions

After stratification according to the size of the lesion and the proportion of solid components in the lesion (\geq 50%, <50%), the eligible subjects were randomized into the new navigation system group (experimental group) and the old navigation system group (control group) in a 1:1 ratio. All included subjects underwent transnavigation-guided bronchoscopic lung biopsy at the respiratory endoscopy center. For pre-biopsy navigation path planning, the small airway reconstruction system-pro (SARS-pro) (self-developed by our team) was used in the experimental group and the conventional VBN system (LungPro; Bronchus Corporation) in the control group. The SARS-pro navigation system is an augmented reality optical navigation system based on VBN, which upgrades the small airway tree reconstruction navigation system through deep learning and multiple trainings.

Outcomes

The primary outcome was the diagnostic positive yield of the different navigation systems for PPL. The second outcome was the adverse events (hemoptysis, pneumothorax, and mediastinal emphysema) of the subjects.

Ethical approval and informed consent statement

The trial was approved by the Ethics Committee of the Sir Run Run Shaw Hospital, Zhejiang University School of Medicine (approval number: 2024-1000) (See the attachment "Ethics Approval Document"). For statistical analysis, subject identities were expressed as codes, which did not involve disclosure of subjects' privacy and personal information, and the study did not involve commercial interests, so informed consent was waived by the Ethics Committee (See the attachment "Informed consent form").

Statistical analysis plan

Official Title of the study: Research on New Intelligent Diagnosis and Treatment Technologies for Early Lung Cancer Based on Multimodal Imaging Bronchoscopy Navigation

Date of the document: May 20, 2024

Research on New Intelligent Diagnosis and Treatment Technologies for Early Lung Cancer Based on Multimodal Imaging Bronchoscopy Navigation

Statistical analysis

For sample size calculation, a study reported a deep learning-based airway segmentation algorithm based on 40 CT images. Based on the benefit of a larger sample size in deep learning, the sample size in this study was set to 100. For subject characteristics, the quantitative data were tested for normality using the skewness and kurtosis methods, and the homogeneity of variance was tested using the Levene test. Normal distribution measurement data were described as mean and standard deviation [Mean (±SD)], and t test or t' test was utilized for comparison between groups. Nonnormal data were summarized as median and interquartile range [M (Q_1 , Q_3)], and group comparisons were made using the Wilcoxon rank sum test. Count data were reported as the number of cases and composition ratio [n (%)], and the chi-square test or the Fisher exact test was utilized for comparison between groups. Data cleaning was accomplished using Python 3.9.12 (Python Software Foundation, Delaware, USA), and the difference comparison was completed by R version 4.3.3 (R Foundation for Statistical Computing, Vienna, Austria). Statistical significance was set to P<0.05.

Data management and confidentiality

(1) The data is stored in the hospital's server with strict security protection and is not accessible to external networks; (2) All information related to the identity of the CT's patients is kept confidential, and the relevant information is not disclosed to the public outside of the scope permitted by relevant laws and/or regulations.

Ethics Committee Approval (Original Chinese version)

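### The new system is meant to work through airways below 3 mm, but the plan never records which lesions need such an airway and makes only one pooled, unadjusted comparison.

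*Combined protocol and SAP*

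**What the plan says.** The Background gives the general performance of the technique as "the overall diagnostic rate of navigation bronchoscopy for biopsy of peripheral lung nodules is 80" per cent, below CT-guided puncture, "especially for near-pleural foci and foci with a diameter of less than 1 cm". It offers three causes: existing software recognises airways under 3 mm poorly, the bronchoscope tip is too wide for the finest airways, and small airways may be collapsed on the planning CT. The new system addresses the first. It is meant to "intelligently recognize more small airway segments smaller than 3mm".

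The inclusion criteria admit peripheral nodules up to 30 mm in mean diameter, with no criterion on airway calibre or distance to the pleura. Under Interventions, randomisation takes place "After stratification according to the size of the lesion and the proportion of solid components in the lesion"; a 50% cut-point is given for solid proportion and none for size. Under Outcomes, "The primary outcome was the diagnostic positive yield of the different navigation systems for PPL". The Statistical analysis section offers a chi-square or Fisher test for count data, under subject characteristics, and no other method that would apply to yield. It contains no covariate adjustment, subgroup or interaction.

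**The concern.** The protocol states a mechanism and then plans no analysis that could examine it. If the benefit runs through small airways, lesions reached by larger ones dilute the pooled difference. A non-significant result would leave two explanations standing: the reconstruction does not help, or too few lesions required it. A significant result could not be linked to the claimed mechanism either.

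A separate and smaller matter is pleural proximity. The protocol associates it with lower yield, yet it is neither balanced nor adjusted for, so a known source of variation in the outcome is left in the comparison.

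**Working it through.** **Plan's own figure.** The SAP states that "the sample size in this study was set to 100", citing that "a study reported a deep learning-based airway segmentation algorithm based on 40 CT images". It gives no yield difference or power, so the 100 cannot be reproduced, and it does not say whether 100 is the total or per arm.

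**Inputs from the documents.** 1:1 allocation; "Statistical significance was set to P<0.05" (taken as two-sided); control yield 80% (a Background figure for the technique in general, not a design assumption).

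**Assumed inputs, not in the documents.** A target lesion is one whose route requires an airway below 3 mm. Share of target lesions f = 0.40 (range 0.30 to 0.50); yield in target lesions 60% control, 85% new system; no difference in other lesions; 50 per arm.

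**Step 1: pooled yields.** Yield in other lesions = (0.80 − 0.60f)/(1 − f). At f = 0.40 this is (0.80 − 0.24)/0.60 = 0.933. Pooled new-system yield = 0.80 + 0.25f = 0.90.

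**Step 2: exact power, uncorrected two-sided 5% chi-square, by enumeration.**

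| f | Yield in other lesions | Pooled yields | Pooled power, 50/arm | Target-lesion power |
|---|---|---|---|---|
| 0.30 | 89% | 80% vs 87.5% | 18% | 35% (15/arm) |
| 0.40 | 93% | 80% vs 90% | 30% | 44% (20/arm) |
| 0.50 | 100% | 80% vs 92.5% | 47% | 53% (25/arm) |

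Holding overall control yield at 80% forces the yield in other lesions to change from row to row; the last row is a boundary case. If 100 means per arm, the pairs are 30% vs 60%, 52% vs 72% and 75% vs 82%.

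**Step 3: sensitivity to the test.** The SAP allows Fisher's test. Using it whenever an expected count is below 5, target-lesion power falls from 35% to 24% at f = 0.30 and from 44% to 42% at f = 0.40. Pooled power barely moves (18% and 30%).

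**Step 4: sensitivity to a gain elsewhere.** At f = 0.40, add a gain g in the other 60% of lesions; pooled new-system yield = 0.90 + 0.60g.
- g = 3 points: 0.918, pooled power 42%.
- g = 5 points: 0.930, pooled power 51%.

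Against 44% in target lesions, the ranking has reversed by 5 points.

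**Step 5: what the subgroup can deliver.** With 20 target lesions per arm, SE = √(0.60×0.40/20 + 0.85×0.15/20) = 0.136, so the 95% half-width is 1.96 × 0.136 = 0.27. In other lesions (30 per arm), SE = √(2 × 0.933 × 0.067/30) = 0.064. The interaction SE is √(0.136² + 0.064²) = 0.150, and power ≈ Φ(0.25/0.150 − 1.96) = 38%.

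**Step 6: chance imbalance.** For a factor with 40% prevalence, the 95% range of the between-arm difference is 1.96 × √(2 × 0.4 × 0.6/50) = ±19 points. With an assumed 20 to 30 point yield gap, the shift at that extreme is 3.8 to 5.8 points.

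**The case against.** The strongest reply is that the pooled question is legitimate. The stated purpose is accuracy in peripheral lesions generally, and a clinician choosing a system wants the overall yield. That stands, and it is why overall yield should remain primary.

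A reader might infer that a subgroup test is simply the more powerful comparison. The documents do not support this. They give no share of target lesions, no yield in them and no expected gain, and the advantage depends on little or no benefit elsewhere. Interventions describes the new system as an augmented-reality optical navigation system, so differences outside the smallest airways cannot be excluded.

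A reader might also equate near-pleural lesions with those where the systems can differ. The Background places subpleural difficulty under the width of the bronchoscope, which planning software does not change. Near-pleural status is therefore supported as a prognostic factor; the requirement for an airway below 3 mm is the supported marker of where the systems may differ.

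Nor is it right that nothing is done about the weak groups. Lesion size, the other one named, is a stratification factor, although it has no cut-point and the SAP does not use it in analysis.

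Finally, the chance imbalance in Step 6 is not a bias. It is already reflected in the standard error of a randomised comparison; adjustment is worth making for precision. And no subgroup analysis repairs a sample size that was not derived from yield.

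**Conclusion.** The point holds as an inexpensive improvement. The plan does not record the lesion feature through which its intervention is said to act, so the pooled result alone cannot distinguish absence of benefit from scarcity of lesions that could benefit; and it leaves a prognostic factor of its own naming unadjusted. Dilution is plausible on the protocol's mechanism, but its size (about 30% pooled power against 44% in target lesions at a 40% share) rests wholly on assumed shares, yields and a confined gain. The omission does not invalidate the pooled comparison, and the subgroup would inform its interpretation without being able to settle the question at this sample size.

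**What to change.** 1. From the planning CT, record for each target lesion its proximity to the pleura and whether the route to it requires an airway below 3 mm. Use one common reading method in both arms, blind to arm and outcome. If each arm's own software were used, the classification would depend on allocation, because the new system is built to show more small airways. Define the item by what the route requires, not by the last airway visible, since by the protocol's account such airways may not be visible.
2. Apply the same reading retrospectively to subjects already enrolled; recruitment began in August 2023 and the plan is dated May 2024. Fix the definitions before outcomes are examined.
3. Keep overall yield as primary, reported as a difference with a 95% CI, adjusted for lesion size and solid proportion (the stratification factors) and for near-pleural status as a prognostic covariate. State the size cut-point. Keep the model small: at 80% and 90% yield with 50 per arm, only 10 + 5 = 15 biopsies are expected to be non-diagnostic.
4. Prespecify as a secondary analysis the yield difference with 95% CI in lesions requiring an airway below 3 mm, with a treatment-by-lesion-type interaction, labelled supportive.

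The cost is two readings of a scan already taken and a few lines of SAP text. The downside is an imprecise subgroup estimate: about 40 subjects if 100 is the total.

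### Does a plan dated 20 May 2024, for a trial recruiting from August 2023, have to change because it does not show when sample size, outcome and tests were fixed?

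*Combined protocol and SAP*

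**What the plan says.** The Study population section of the protocol gives the recruitment period: subjects were "recruited from August 2023 to December 2024 at the Sir Run Run Shaw Hospital". The protocol header and the SAP header both read "Date of the document: May 20, 2024". The supplied text has no version number, amendment log or earlier version.

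Three elements would need to be fixed in advance:

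- **Primary outcome** (protocol, Outcomes): "The primary outcome was the diagnostic positive yield of the different navigation systems for PPL".
- **Sample size** (SAP, Statistical analysis): "the sample size in this study was set to 100". No effect size or power is given, and no date on which the number was chosen.
- **Tests** (SAP, Statistical analysis): for count data, "the chi-square test or the Fisher exact test was utilized for comparison between groups". The run of test descriptions opens with subject characteristics, and no sentence ties a test to diagnostic yield by name.

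The same SAP section says that "the difference comparison was completed by R version 4.3.3". The Interventions section says that the new system, "self-developed by our team) was used in the experimental group", was compared with a commercial one. The ethics statement cites an approval number beginning with 2024 and refers to approval and consent attachments that are not in the supplied text.

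**The concern.** On the dates as printed, more than half of the recruitment period had passed when the plan was dated. Biopsy results become known soon after each procedure, the trial is at one centre, the experimental system is the team's own, and no blinding to accruing results is described. If results by arm were visible when the number of subjects, the outcome or the test was chosen, those choices could have followed the data, and the nominal 5% error rate could not be claimed.

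The past tense sharpens the suspicion. A document dated May 2024 reports recruitment to December 2024 and describes the comparison as done, so either the text is later than its date or planned steps were written as completed ones.

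The plan also seems to leave room to manoeuvre. It allows chi-square or Fisher without a rule for choosing. At 50 per arm, 40/50 against 47/50 gives P = 0.037 by uncorrected chi-square and P = 0.071 by Fisher, on opposite sides of the threshold.

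**Working it through.** **1. Dates.** Inputs: recruitment from August 2023 to December 2024 (protocol, Study population) and the document date of 20 May 2024 (both headers). The first and last days are not given, so each month is taken at both ends. Share elapsed = (plan date − start) / (end − start).

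| Start | End | Days to plan date | Days in window | Share | Days from plan date to end |
|---|---|---|---|---|---|
| 1 Aug 2023 | 1 Dec 2024 | 293 | 488 | 60.0% | 195 |
| 1 Aug 2023 | 31 Dec 2024 | 293 | 518 | 56.6% | 225 |
| 31 Aug 2023 | 1 Dec 2024 | 263 | 458 | 57.4% | 195 |
| 31 Aug 2023 | 31 Dec 2024 | 263 | 488 | 53.9% | 225 |

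If accrual were uniform and 100 is the number randomised (both assumptions), 54 to 60 subjects precede the plan date and 40 to 46 follow it. The factual part of the concern is correct.

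**2. What the past tense proves.** December 2024 lies after the document date. If the date is right, the end of recruitment is a plan written in the past tense, and the statement that the comparison was completed may be no more than that. The file closes with an ethics approval headed as an original Chinese version, so translation style is a plausible explanation. If the date is wrong, it says nothing about when choices were made. On neither reading does the tense show that results had been examined. What survives is the August 2023 start.

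**3. What the open choice of test costs.** Assume 50 per arm (100 split 1:1) and a two-sided 5% level. Enumerate every pair of counts (a, b), each from 0 to 50, with binomial probabilities at a common yield p. The chi-square statistic is 100·[a(50−b) − b(50−a)]² / [50·50·(a+b)·(100−a−b)].

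- Every table that Fisher rejects is also rejected by uncorrected chi-square. Taking the smaller of the two P values therefore rejects exactly the same tables as uncorrected chi-square alone.
- The resulting false-positive rate is 5.7% at p = 50%, 5.2% at 80% and 4.3% at 95%. Over the yields tried between 50% and 95% it stays within 4.3% to 5.7%. The 80% figure is the background yield in the protocol.
- In the 40/50 against 47/50 example the smallest expected count is 50 × 13/100 = 6.5, so the usual expected-count rule selects chi-square. With a continuity correction the chi-square P value is 0.074, on Fisher's side. The contrast depends on one version of one test in one chosen table.

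This freedom is also unrelated to dating: a plan dated July 2023 with the same sentence would have it too.

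**4. Whether splitting the data at the plan date would help.** With 40 to 46 later subjects there are 20 to 23 per arm. The 95% half-width is 1.96·√(p₁q₁/n + p₂q₂/n), with 80% in one arm and an assumed 80% or 90% in the other:

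- n = 20: 24.8 points (80 v 80) and 21.9 points (80 v 90).
- n = 23: 23.1 and 20.4 points.
- n = 50, for comparison: 15.7 and 13.9 points.

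Power for 80% against 90% in the later subset is 14% to 16%. Such a table could neither confirm nor refute an effect, and if 20 May 2024 is only a filing date the cut is arbitrary.

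**The case for a change.** The strongest case for a change is that a late plan does little harm when it is tight, and this one is not. What counts as a positive diagnosis is not defined, no test is assigned explicitly to the primary outcome, and 100 rests on a segmentation study of 40 CT images rather than on a target difference. One exclusion, missing visits after biopsy, can only be applied afterwards. With no dated earlier version and no statement on access to results by arm, a reader cannot rule out that these choices followed the data. Asking for a few dated sentences costs almost nothing.

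Much of this stands. The record is incomplete, only the sponsor can complete it, and it should be completed. But the loose outcome definition, the basis for the sample size and the exclusions are separate questions that would arise whatever the date on the plan. On timing itself, the objection shows missing evidence and not a faulty rule. It also has to allow that attachments were removed before review, so the documents seen are the only ones supplied and not necessarily the only ones that exist.

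The ethics statement, "the study did not involve commercial interests, so informed consent was waived by the Ethics Committee", has also been set against the randomised design. That is an ethics question, it depends on the missing attachments, and it has no bearing on pre-specification.

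**Conclusion.** No change to the plan follows. The plan date falls 54% to 60% of the way through the stated recruitment window, and the supplied text does not say when the sample size, outcome and tests were fixed. This is a gap in documentation. The plan does not claim to predate enrolment, no statement shows that arms were compared before May 2024, and reconciling the dates would leave every outcome, test and threshold as written.

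The gap is one that the analysts can fill when they report: the date of first randomisation, the date on which the design choices were settled, any version that predates recruitment, and whether results by arm had been seen by then. If that last point cannot be stated, readers should treat the P<0.05 comparison as exploratory. That affects how the result is described and not how it is computed.

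The conclusion rests on the dates as printed and on the past tense being no proof of analysis. The test-choice result (4.3% to 5.7%) assumes 50 per arm, a two-sided 5% level and common yields from 50% to 95%. The estimate of 54 to 60 subjects before the plan date further assumes uniform accrual.

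### Does admitting patients with several nodules let each arm's own path planning decide which nodule counts towards the primary yield?

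*Combined protocol and SAP*

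**What the plan says.** The protocol's Inclusion and exclusion criteria allow "patients with one or more peripheral lung nodules suspected to be lung cancer". The other criteria then speak of a nodule or lesion in the singular.

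Under Interventions, subjects are randomised 1:1 "After stratification according to the size of the lesion and the proportion of solid components in the lesion". Path planning comes next and differs by arm: "For pre-biopsy navigation path planning, the small airway reconstruction system-pro (SARS-pro) (self-developed by our team) was used in the experimental group", with the conventional virtual bronchoscopic system in the control group.

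Under Outcomes, the primary endpoint is the "diagnostic positive yield of the different navigation systems for PPL". It names no index nodule and does not say whether the denominator is patients or nodules.

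The SAP's Statistical analysis section adds only general rules: "Count data were reported as the number of cases and composition ratio", and "the chi-square test or the Fisher exact test was utilized for comparison between groups".

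**The concern.** Three features together look troublesome. A patient may bring several nodules. The endpoint does not say which one is scored. The step that determines whether a nodule can be reached is the randomised intervention itself.

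The protocol's Background supplies a mechanism. It says that mainstream CT-based navigation misses some small airways, "resulting in failure or inaccuracy of preoperative bronchoscopic path planning in some areas", and of the marketed systems, the control system included, that "all of them are suboptimal for the reconstruction of small airways less than 3 mm". In a two-nodule patient a failed plan might move the biopsy to a more accessible nodule. If that second nodule were scored, the failure would vanish from the yield, and more often in the control arm. The contrast the trial exists to measure would be blurred by a choice made after allocation.

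A second worry is that two nodules from one patient might be entered as independent observations in a chi-square test.

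**Working it through.** **Reading the text in order.** For subjects to be stratified on lesion size and solid proportion, a lesion must have been selected and measured first. Randomisation follows, and only then is a path planned with the allocated system. So the lesion behind the stratification values is known before the arm is. The Background passage on planning failure explains why diagnostic rates are lower; it does not describe moving to another nodule. Nothing states that a switch occurs, and nothing excludes one.

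**Size if switching did occur.** The plan has no figure of its own to reproduce here. It gives a background diagnostic rate of 80% and a sample size of 100. The rest is assumed: 50 patients per arm; yield p = 0.80 once a nodule is reached, in both arms; stratification nodule unreached in uE = 5% of the experimental arm and uC = 10%, 15% or 20% of controls; a share s of patients with a second, reachable nodule.

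- Yield on the stratification nodule: (1 − u)p, so the difference is (uC − uE)p.
- Yield on the nodule biopsied: (1 − u)p + u·s·p, so the difference is (uC − uE)p(1 − s).

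Difference between arms, in percentage points:

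| uC | Stratification nodule | Biopsied, s = 10% | s = 20% | s = 50% |
|---|---|---|---|---|
| 10% | 4.0 | 3.6 | 3.2 | 2.0 |
| 15% | 8.0 | 7.2 | 6.4 | 4.0 |
| 20% | 12.0 | 10.8 | 9.6 | 6.0 |

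The loss is 0.4 to 1.2 points at s = 10% and 2.0 to 6.0 points at s = 50%. It is zero if nobody has two nodules or nobody switches.

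**Against the trial's precision.** The half-width is 1.96·√[(pC·qC + pE·qE)/50]. For 72% v 76% it is 1.96·√(0.3840/50) = 17.2 points; for 64% v 76% it is 1.96·√(0.4128/50) = 17.8 points. The largest loss, 6.0, is about a third of the half-width (6.0/17.8 = 0.34). At s = 10% the largest loss, 1.2, is about 7% of it.

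**Varying the assumptions.**

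- Second nodule unreached as often as the first: the loss is s·p·[uC(1 − uC) − uE(1 − uE)]. This runs from 0.1 × 0.8 × (0.09 − 0.0475) = 0.3 points to 0.5 × 0.8 × (0.16 − 0.0475) = 4.5 points.
- The Background gives 80% as an overall rate, not a rate once reached. Rescaled, p = 0.80/0.90 = 0.89 at 10% unreached, with a loss at s = 10% of 0.1 × 0.05 × 0.89 = 0.4 points. At 20% unreached p = 0.80/0.80 = 1.00, with a loss at s = 50% of 0.5 × 0.15 × 1.00 = 7.5 points. That last case requires every reached nodule to be diagnosed.
- Equal true yield per nodule in both arms, but unequal tendency to take the easier nodule: the spurious difference is the multi-nodule share × the between-arm difference in taking the easier nodule × (easier − harder yield). With yields of 90% and 60%, 0.1 × 0.25 × 0.30 = 0.8 points and 0.4 × 1 × 0.30 = 12.0 points. The chance of rejecting at the 5% level is 5.1% and 40.7% respectively. The second case needs 40% of patients to have several nodules, and every one of them to take the easier nodule in one arm and none in the other.

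**The test.** With one result per subject the observations are independent, and chi-square or Fisher is appropriate. Clustering matters only if nodules are counted separately, which the SAP does not propose.

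**The case for a change.** The best case for a change is that a primary endpoint should not depend on a reader inferring its unit. Singular wording and the order of steps suggest one target per subject, but they do not define it, and an undefined endpoint leaves the choice open until results are known. The direction of any bias follows from the sponsor's own account of the control system. Excluding patients judged unlikely to benefit from bronchoscopic biopsy would not remove it, because that criterion does not mention failed small-airway planning. A sentence naming the scored nodule would settle the matter.

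Much of this stands: the definition is missing, and the conditional arithmetic is right. The step from a missing definition to a biased comparison does not. It needs the target to change after planning, the substitute to be scored, and enough multi-nodule patients for this to matter. The documents give none of the three.

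Nor is a late definition quite free. Recruitment began in August 2023 and the SAP is dated May 20, 2024. For multi-nodule subjects already enrolled, the recorded size and solid category may not identify which nodule was meant, so some scans might have to be read again.

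**Conclusion.** No change is called for. The plan leaves a definition unwritten; it does not state a rule that gives a wrong answer. The natural completion is one result per subject, on the lesion characterised for stratification. That lesion is fixed before allocation, so arm-specific planning cannot select it, and the planned tests apply as written.

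The residual risk is conditional. If targets were switched and the substitutes scored, the main model gives an attenuation of 0.4 to 1.2 points at a 10% share of patients with a second reachable nodule and at most 6.0 points at 50%, against a half-width of 17.2 to 17.8 points. Less favourable assumptions give larger values, but they need conditions for which the documents offer no support. All of these sizes rest on assumed reach rates, multi-nodule shares and switching behaviour. A reader of the results would still want to be told how many subjects had several nodules and whether any target changed, which is ordinary reporting.
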